Delineate clinical procedures from research procedures. Will subject's insurance (or subject) be responsible for research related costs? If so state for which items subject's insurance (or subject) will be responsible (surgery, device, drugs, etc). If appropriate, discuss the availability of financial counseling.

We do not anticipate that the research subjects will incur any cost by participating in this study.

If subjects will be paid (money, gift certificates, coupons, etc.) to participate in this research project, please note the total dollar amount (or dollar value amount) and distribution plan (one payment, pro-rated payment, paid upon completion, etc) of the payment.

Dollar Amount:

0

Distribution Plan:

Section M: Genetics

How would you classify your genetic study?

Discuss the potential for psychological, social, and/or physical harm subsequent to participation in this research. Please discuss, considering the following areas: risks to privacy, confidentiality, insurability, employability, immigration status, paternity status, educational opportunities, or social stigma.

Will subjects be offered any type of genetic education or counseling, and if so, who will provide the education or counseling and under what conditions will it be provided? If there is the possibility that a family's pedigree will be presented or published, please describe how you will protect family member's confidentiality?

Section N: Sample Collection

None

Section O: Drug Studies

Does the research involve the use of ANY drug* or biologic? (*A drug is defined as any substance that is used to elicit a pharmacologic or physiologic response whether it is for treatment or diagnostic purposes)

No

Does the research involve the use of ANY gene transfer agent for human gene transfer research?

O1. Current Drugs

Is this study placebo-controlled?

No

Will the research involve a radioactive drug?

No

Section P: Device Studies

Does this research study involve the use of ANY device? Yes

Device 1: Sonosite X-Porte

Device 2: Sonosite Edge II

Device 3: Sonosite M-Turbo

Section Q: Consent Form(s)

Ultrasound transducer selection comparison in the FAST exam

Ultrasound transducer selection in the FAST exam - Healthy normal volunteer

Section R: Advertisements

None

## **Background**

The Focused Assessment of Sonography for Trauma (FAST) is a rapid point-of-care ultrasound exam performed on blunt and penetrating trauma patients who are too critically injured to be transported to a CT scanner. In performing this exam, time to acquisition of adequate images is crucial to clinical decision-making as patients undergoing this exam have a high probability of deteriorating if not intervened on appropriately.

Low-frequency ultrasound is used to image the abdominal cavity in these patients, using either a curvilinear transducer or a phased-array transducer. Both of these transducers are capable of acquiring the images necessary to interpret a FAST exam, but it has not been studied whether using one transducer instead of the other improves time to image acquisition or image quality.

In this study, we will recruit ultrasound operators (trained emergency medicine residents, faculty, or advanced practice providers) and healthy participants on which the ultrasound exam will be performed. We will ask the ultrasound operators to perform the FAST exam using different types of ultrasound transducers on the healthy test patients.

### **Study Outcomes**

In this study, the following data will be collected:

- Baseline characteristics of each participant (demographic information, training level, prior experience with performing FAST ultrasounds if known)
- Time to completion for each FAST exam performed with a phased-array transducer and for a curvilinear transducer, from start to completion of the exam
- Technical quality of each of the four required views of the FAST exam (subxiphoid, right upper quadrant, left upper quadrant, and suprapubic view)

The primary outcome of this study is time to FAST exam completion. The secondary outcome is technical quality of the ultrasound images.

#### **Arms of the Study**

This study has two arms being compared. The first arm is the phased-array transducer arm, which collects the above mentioned outcomes for. The second arm is the curvilinear transducer arm. Each ultrasound operator will be randomized to one of the two arms to begin with. There will be no blinding of the participants or of the study investigators. After each participants completes their FAST ultrasound, they will cross-over to the other arm of the study. Thus, each participant will perform two FAST exams, one with each type of transducer.

## **Statistical Analysis**

For the primary outcome of time to completion of the ultrasound exam, we will report descriptive statistics for each arm. We will report any differences between these descriptive statistics for each type of transducer. If there are enough participants in each subgroup to make meaningful comparisons, we may also report subgroup descriptive statistics based on the training level of the participants.

We will perform a t-test to analyze the two arms for differences in mean time to completion of each ultrasound. Additional subgroup comparisons based on the level of training of participants may be performed.

For the secondary analysis, Fisher's exact test will be used to determine if there is a statistically significant difference between the numbers of technically adequate for interpretation ultrasound exams performed for each arm. A numeric scale for quality of the images may also be used, and if so, a t-test to analyze differences in numeric scale rating of image quality between the two arms will be used.

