Our population, which includes both subjects that will perform the exam and will have the exam performed on them, will include women of child bearing potential. However, abdominal and cardiac ultrasonography is generally recognized as safe, with no known long-term adverse health effects. We do not anticipate a negative effect of the performance of these ultrasound exams on the health of our subjects or their future child-bearing potential. Human model patients who are pregnant will be excluded from the study.

We will be recruiting residents and faculty in this study. Study participation and data will not affect participant evaluations or consideration of employment status and this will be reflected on the written informed consent. We will take measures to de-identify the study data and prevent future re-identification of the study data. We will not recruit individuals who have limited decision-making capacity.

E3. Pregnant woman/fetus

Will pregnant women and/or fetuses (as described in 45 CFR 46 Subpart B) be enrolled in the research?

E4. Neonates

Will neonates of uncertain viability or nonviable neonates (as described in 45 CFR 46 Subpart B) be enrolled in the research?

No

E5. Children

Will children be enrolled in the research?

No

Section F: Design/Procedure

F1. Design

Select one category that most adequately describes your research:

c) Pilot

Discuss the research design including but not limited to such issues as: probability of group assignment, potential for subject to be randomized to placebo group, use of control subjects, etc.

Participants will be block-randomized to a group A and group B. For the purposes of this text, the term "operators" will refer to the participants who are performing the ultrasound exam. The term "patients" will refer to the healthy volunteers with no medical conditions who will have the ultrasound exam performed on them.

Group A will conduct an ultrasound exam on one patient using a curvilinear transducer, and group B performs the exam on another different patient using a phased-array transducer. After each operator performs their examination, they will cross-over, performing the same exam using the other transducer on the other patient.

Inclusion Criteria:

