Emergency medicine residents (PGY 1-3), emergency medicine PA fellows, and emergency medicine faculty at Baylor College of Medicine will be recruited as operators. Healthy, non-pregnant emergency medicine faculty members recruited from Baylor College of Medicine who sign a written informed consent to be the subjects of the ultrasound examination will be used as the model patients.

Exclusion Criteria:

Pregnant women, adults over age 64, individuals younger than 18, and any individuals who elect not to participate or who withdraw their consent at a later date.

F2. Procedure

The FAST exam is part of standard clinical care of the trauma patient and consists of four views of the thorax and abdomen acquired with an ultrasound transducer. These views are: subxiphoid images of the heart; right upper quadrant images of the hepato-renal recess and right paracolic gutter; left upper quadrant images of the spleen-diaphragm interface, spleno-renal recess, and left paracolic gutter; and suprapubic images of the bladder and recto-vesicular or recto-vaginal pouch. Each operator will perform two ultrasound exams each with a different type of ultrasound transducer. The performance of ultrasound exams is part of standard clinical training of emergency medicine practitioners and medical students, and is considered a procedure with minimal risk to both the operator and patient. No part of the actual ultrasound exam being performed that is described here is investigational; all parts of this exam, performed with either the phased array or curvilinear probe, are considered the current standard of care for unstable trauma patients.

Prior to the ultrasound procedure we will administer a pre-survey to each participant. This survey will assess their knowledge of the adequate views of the FAST exam, their level of experience with the use of curvilinear and phased array probes, and their general level of ultrasound experience.

Each patient will be fasted for three hours prior to the exam.

Operators randomized to group A will perform an ultrasound exam on a patient using a phased-array transducer, and operators randomized to group B will perform an exam on the other patient using a curvilinear transducer. Both exams will be a complete FAST exam and each of the four exam components will be timed. After each subject in each group completes their FAST exam, they will cross-over.

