The time to complete image acquisition of each of the four parts of the FAST exam will be collected for each subject with each transducer. The ultrasound images acquired for each transducer and each view will also be evaluated to assess them for quality of the acquired images, which will be graded as either adequate (sufficient for interpretation in a real patient) or inadequate (insufficient for interpretation in a real patient).

Section G: Sample Size/Data Analysis

G1. Sample Size

How many subjects (or specimens, or charts) will be used in this study?

Local: 40 Worldwide: 40

Please indicate why you chose the sample size proposed:

This is a convenience sample of the number of expected residents, PA fellows, and faculty that we expect to participate.

G2. Data Analysis

Provide a description of your plan for data analysis. State the types of comparisons you plan (e.g. comparison of means, comparison of proportions, regressions, analysis of variance). Which is the PRIMARY comparison/analysis? How will the analyses proposed relate to the primary purposes of your study?

Time to completion of each part of the ultrasound exam, total time to completion of the ultrasound exam, and whether or not the ultrasound exam is adequate or inadequate is the dependent variable. The independent variable is the type of ultrasound transducer (curvilinear or phased array) used for the ultrasound exam. The mean values of the time to completion will be compared in this data analysis and analyzed for significance, and whether or not the exam was adequate or inadequate will be compared (through a Fisher's exact test) to determine if there is a significant difference between the curvilinear transducer and the phased array transducer groups.

The primary comparison/analysis is the time to exam completion. The secondary comparison/analysis is

whether or not the exam was adequate. This analysis will determine if the hypothesis of the study, that there is a significant difference in time to completion and adequacy of the ultrasound exam, is supported or refuted.

Section H: Potential Risks/Discomforts

H1. Potential Risks/Discomforts

Describe and assess any potential risks/discomforts; (physical, psychological, social, legal, or other) and assess the likelihood and seriousness of such risks:

This protocol does not include exposure to ionizing radiation.

There are several risks for discomfort.

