## **Summary**

Each participant will be randomized to one of two arms, where they will perform a FAST exam on a healthy volunteer for the purposes of determining if there is a difference in the time to completion or the imaging quality of a phased-array transducer or curvilinear transducer for this application.

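### The primary t-test is not specified as paired or adjusted for period, although every operator contributes to both arms; run unpaired, it could lose much of the crossover's precision.

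*SAP*

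**What the plan says.** - **Design.** The SAP (Arms of the Study) randomises each operator to a starting transducer and then crosses them over: "Thus, each participant will perform two FAST exams, one with each type of transducer". Protocol F1 describes the same crossover, with the model patient changing too: "performing the same exam using the other transducer on the other patient".
- **Primary analysis.** The SAP (Statistical Analysis) says: "We will perform a t-test to analyze the two arms for differences in mean time to completion of each ultrasound". Protocol G2 says only that mean completion times will be compared between the transducer groups.
- **Numeric quality score, if used.** The same form of test is planned: "a t-test to analyze differences in numeric scale rating of image quality between the two arms will be used".
- **Summary.** The SAP closes with wording that would suit a parallel-group trial: "Each participant will be randomized to one of two arms, where they will perform a FAST exam on a healthy volunteer".
- **Use of the result.** Protocol G2 says the analysis of time and adequacy will settle whether the hypothesis, "that there is a significant difference in time to completion and adequacy of the ultrasound exam, is supported or refuted".

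Neither document mentions pairing, within-operator differences, period or sequence. Neither says that the samples are treated as independent.

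**The concern.** The two completion times from one operator share that operator's skill and speed. Operators range from PGY-1 residents to faculty (Protocol F1, Inclusion Criteria), so a positive within-operator correlation is plausible. A crossover is chosen to remove that variation from the comparison. An independent-samples t-test puts it back.

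A second, smaller source of noise is practice. If operators are faster on their second exam, a plain paired test leaves that shift in its error term. If the two sequences also end up unequal in size, the shift biases the estimate.

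This is the primary analysis in an unblinded study. Two analysts could follow the same sentence, run different t-tests and reach different conclusions. The choice should not be open once the data can be seen.

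**Working it through.** **Inputs from the documents.** 40 subjects (Protocol G1), a convenience sample. G1 does not say whether the model patients are counted, so 38 operators were also tried. Two exams per operator. Block randomisation to sequence, ratio not stated (F1). There is no power calculation to reproduce.

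**Assumptions.** Two-sided 0.05; total SD of an exam time = 1; true transducer difference 0.4 SD; within-operator correlation ρ from 0 to 0.7; practice effect 0 or 0.5 SD; no difference between model patients. None of these values is in the documents.

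**Standard errors, n = 40.**
- Unpaired: √(2/n) = √(2/40) = 0.224 SD, whatever ρ is.
- Paired: √(2(1−ρ)/n) = 0.187, 0.158 and 0.122 SD at ρ = 0.3, 0.5 and 0.7.
- Ratio: 1/√(1−ρ) = 1.20, 1.41 and 1.83.

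**95% CI half-widths.** Unpaired, 78 df: 1.991 × 0.2236 = 0.445 SD. Paired, 39 df: 2.023 × SE = 0.378, 0.320 and 0.248 SD.

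**Power and type I error.** Unpaired figures are simulated with a random operator effect. Paired figures agree with the noncentral t (55.0%, 69.4% and 89.0% at ρ = 0.3, 0.5 and 0.7).

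| ρ | SE ratio | Power unpaired | Power paired | Unpaired type I error |
|---|---|---|---|---|
| 0 | 1.00 | 42% | 41% | 5% |
| 0.1 | 1.05 | 42% | 45% | 3.9%* |
| 0.2 | 1.12 | 41% | 49–50% | 2.8%* |
| 0.3 | 1.20 | 41% | 55% | 2.0% |
| 0.5 | 1.41 | 39% | 69% | 0.65% |
| 0.7 | 1.83 | 37% | 89% | 0.06% |

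*Normal approximation.

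With 38 operators at ρ = 0.3, 0.5 and 0.7, power is 39% v 53%, 37% v 67% and 34% v 87%.

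**How often the choice of test changes the result (n = 40).** At ρ = 0.3, 0.5 and 0.7 the paired test is significant and the unpaired test is not in 14%, 30% and 52% of simulated trials. The reverse occurs in under 0.2%.

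**Period, with a practice effect of 0.5 SD and ρ = 0.5.** With a 20/20 split, the within-operator difference has variance 2(1−0.5) = 1, plus 0.5² × 40/39 = 0.256 from practice. The plain paired standard error therefore rises by √1.256 = 1.12. With unequal sequences, the bias from ignoring period is practice effect × (n₁−n₂)/n; at 22/18 this is 0.5 × 4/40 = 0.05 SD.

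| Split | Unpaired | Paired | Period-adjusted | Bias if period ignored |
|---|---|---|---|---|
| 20/20 | 36% | 61% | 69% | none |
| 22/18, bias against the difference | 25% | 49% | 69% | −0.05 SD |
| 22/18, bias towards the difference | 48% | 72% | 69% | +0.05 SD |

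**Can a model-patient term be added?** In the two-patient layout of Protocol F1 each transducer stays with one patient. A design matrix with intercept, transducer, period and patient then has rank 3 with 4 columns, so patient and transducer cannot be separated. Without patient it has rank 3 with 3 columns, and the transducer effect is estimable.

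**The case against.** The best reply is that the plan is silent rather than wrong. A paired t-test is a t-test, the SAP states plainly that each operator does two exams, and its use of the word arm for each condition of a crossover says nothing about the test. The Summary is a one-sentence recap. Fisher's exact test by arm does assume independence, but it concerns the secondary outcome. All this is fair: the documents do not commit to an unpaired test. They do not rule it out either, and a primary analysis should.

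The second reply is that the loss depends on a correlation nobody has stated. This stands. At ρ of 0.2 or less the unpaired standard error is at most 12% too large and the power gain is under 10 points. But a paired, period-adjusted analysis costs only about one point of power even at ρ = 0, so the uncertainty is no reason to avoid it.

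Third, period adjustment matters less than pairing. This also stands. With no practice effect it changes almost nothing, with equal sequences it removes only noise, and block randomisation makes a large imbalance less likely.

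Fourth, this is a pilot with no promised power. That limits the severity, but Protocol G2 still uses the analysis to judge the hypothesis.

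Finally, the power figures assume no difference between model patients. If each transducer stays with one patient, any patient difference enters the contrast under every test compared here. Pairing does not cure that.

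**Conclusion.** The concern holds and should be fixed. The omission is certain: neither document specifies pairing or period for a primary comparison in which every operator supplies both measurements. The size of the loss is conditional on the test being run unpaired and on the assumed correlation. At ρ = 0.5 the interval is about 1.4 times as wide as it need be (0.445 v 0.320 SD) and power for a 0.4 SD difference is 39% instead of 69%; at ρ of 0.2 or below the loss is minor. With positive correlation the unpaired test rejects too rarely under the null, so the harm is missed differences, wide intervals and a result that depends on an unstated choice. No promised power is missed, because none was stated.

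**What to change.** 1. In the SAP, define the primary analysis as a within-operator comparison of total exam time adjusted for period. Either a period-adjusted paired t-test, or a mixed model with fixed transducer and period effects and a random operator effect, will do.
2. Report the mean within-operator difference with its 95% CI.
3. Use the same analysis for any numeric image-quality score.
4. Reword the SAP Summary so that it describes a crossover.
5. Do not add a fixed effect for model patient under the layout in Protocol F1, where it is fully aliased with transducer. It could be fitted only if patient–transducer pairings vary.
6. Before coding sequence and period, reconcile the two accounts of group A's first exam. Protocol F1 says "Group A will conduct an ultrasound exam on one patient using a curvilinear transducer", while F2 says "Operators randomized to group A will perform an ultrasound exam on a patient using a phased-array transducer".

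The cost is wording, provided the order of each operator's exams is recorded. Period uses one degree of freedom: 38 instead of 39 with 40 operators.

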## **Summary**

Each participant will be randomized to one of two arms, where they will perform a FAST exam on a healthy volunteer for the purposes of determining if there is a difference in the time to completion or the imaging quality of a phased-array transducer or curvilinear transducer for this application.
